Starting in Year 2, in a 2-arm RCT, we will pilot the *SnappyHour* intervention versus a control group (n=50-52 per group) among EAs with HID (balanced on sex and age group). Screened, eligible participants will complete baseline measures, their assigned condition for 8 weeks, a 2-month (after intervention-start) post-test after the active intervention period (to measure intervention acceptability, changes in outcomes during the intervention period, and mechanisms of change), and a 4-month (after intervention-start) outcomes assessment.

Enrollment: Target enrollment is 102 EAs (approximately 50% males and 50% females) between the ages of 18-25. We will conduct a 2-arm pilot RCT of the Snapchat intervention versus a control group (n=50-52 per group) among EAs with HID (balanced on sex and age group). We will enroll participants in 3-4 waves to allow breaks between 8-week intervention periods for staff.

Recruitment and Study Procedure. Recruitment and enrollment procedures will follow those used in Aim 1 above. To ensure representation of both sexes we will recruit approximately 50% males and 50% females. Using a similar approach to the National Epidemiologic Survey on Alcohol and Related Conditions (NESARC), we will attempt to oversample minorities who are African American and Hispanic (~20%). Thus, we expect approximately 67% Caucasian, 20% African American, 3% Asian, 1% Native American/Alaskan Native, 1% Hawaiian/Pacific Islander, and 8% more than 1 race and 20% Hispanic.

Study participants will be recruited via SM advertisements that appears on social media applications (e.g., primarily Snapchat, but Instagram, Facebook etc., as needed). Ads will be targeted to U.S users ages 18-25. When users swipe up or click on an advertisement, they will be redirected to a privacy notice (as required by Snapchat, our primary recruitment modality), and subsequently, a screening informed consent page. After indicating their agreement to the consent online (with a waiver of parental consent for states with age of majority >18 and a waiver of documentation of consent given our online procedures) and completing a captcha (to protect against bots), participants will complete a ~5-min eligibility survey.

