If participants respond to snaps of intervention content, coaches will use MI skills⁶⁸ (e.g., reflections, open questions, affirmations) to reply during shifts, which will primarily be in the afternoon and evening, based on participant feedback in Aim 1. Coaches will be trained in collaborative MI strategies to manage sustain talk, if any arises. Coaches will have access to on-call supervisors experienced in MI, including Drs. [name] and [name], the study coordinator, and our lab network of clinical post-docs and social workers. All on-call supervisors have experience managing risk assessments (e.g., suicidal ideation) using procedures from our current online intervention study, where staff private message and talk by phone to participants in high risk situations. See DSMP for more details.

Table 1. Measures

Descriptive Information, Individual and Social Influences	
Demographics (from Youth Risk Behavior Survey ¹⁴⁶)	S, B, P, F
Social media involvement ¹⁴⁷	S, P, F
Drinking Motives Questionnaire Revised Short Form ¹⁴⁸	B, P, F
Alcohol Expectancy Questionnaire Adolescent Brief ¹⁴⁹	B, P, F
Perceived risk of HID modified from MTF ¹⁴⁴	B, P, F
Readiness to change alcohol use ^{150, 151}	B, P
Mental health: Patient Health Questionnaire-8	B, P, F
Generalized Anxiety Disorder-7	
Protective Behavioral Strategies Scale-20 ¹⁵⁸	B, P, F
Peer use of alcohol/HID based on MTF ¹⁴⁴	B, P, F
Alcohol online norms and exposure ^{74, 159}	B, P, F
AUDIT-C	S, P, F
Short-Form PCL-5	B, P, F
UCLA Loneliness Scale	B, P, F
Berkman-Syme Social Network Index (SNI)	B, P, F
COVID-19	B, P, F
Choices for Intervention Topics	B
Strengths and Goals	B
Minute Discounting Task	S, P, F
Brief Assessment of Alcohol Demand	S, P, F
Activity Level Questionnaire	B, P, F
Other Outcomes	
Past-Month HID (eligibility criteria) based on MTF ¹⁴⁴	S, P, F
Brief Young Adult Alcohol Consequences ¹⁶⁵	B, P, F
Alcohol-impaired driving ¹⁶⁶	B, P, F
Daily Drinking Questionnaire	B, P, F
Tobacco and Nicotine use	S, P, F
Cannabis frequency (by modality)	S, P, F
Frequency of Illicit Drugs	B, P, F
Frequency of Rx Drug Misuse	B, P, F
Feasibility/Acceptability of Intervention	
Intervention acceptability ratings	P
Control acceptability ratings	P

S=Screening, B=Baseline, P=2 month post-test, F=4-month follow-up

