We will provide documentation of IRB approval for all study procedures prior to beginning screening participants.

- 11. Provide the analysis plan including the power calculation(s). There should be discussion of any planned interim and/or futility analyses, including adjustments for allocating "alpha" on "multiple looks" at the data.**

Specific Aim 1. Intervention development will consist primarily of identifying preferences for content delivery and content with superior ratings, and thus will not involve formal statistical inference. We will conduct descriptive analyses of participants' data regarding preferences, leading to refinements in intervention content.

Specific Aim 2. Analyses pertaining to primary outcomes of feasibility and acceptability of the intervention are primarily descriptive in nature (e.g., % completing the assigned intervention condition, % engaging in Snapchat messaging, ratings of intervention satisfaction). To examine other outcomes related to estimating intervention efficacy, in Aim 2, randomized participants will be included in intent-to-treat analyses, regardless of engagement. By design, groups will be balanced on sex and age; we will validate randomization by evaluating covariate balance between groups. If significant differences that could confound treatment effect estimates emerge, we will adjust for those variables or stratify analyses.

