Testing for Intervention Effects. We will first compare groups outcomes of HID frequency and alcohol-related consequences using basic two-sample comparisons, operating on the pre-post differences (e.g., 4M-Baseline) to test for treatment effects. Our first choice will be a two-sample *t*-test to compare the pre-post differences between groups; considering non-parametric alternatives as needed. We will use generalized linear mixed models (GLMMs) to jointly study the 2M and 4M outcomes while adjusting for correlations between data points (e.g. repeated measurements on individuals). While baseline adjustment is important for guarding against regression to the mean in RCTs, such adjustment at every time point may overestimate the treatment effect when there are multiple follow-ups. Baseline adjustment at only the first follow-up (2M in this case) corrects this overestimation while also guarding against regression to the mean, which will be our approach. Within this framework, the treatment effect is estimated by the treatment group indicator in the regression model. We will conduct exploratory sub-analyses of whether the intervention effect is accumulating or weakening over time, by including time-by-group interactions. If we ascertain the need, we will control for confounders through their inclusion in the model as covariates. Overall, this approach is effectively the same as the ANCOVA method of RCT analysis, but modified to account for multiple follow-ups and possibly inhomogeneous treatment effects (e.g. time-varying or modified by other factors, see secondary aims, below). Our initial specification will be a linear mixed effects model (with Gaussian error distribution) with only a random intercept to capture within-individual dependence, but we will scrutinize this choice by examining model diagnostics. If we ascertain the need, we will examine other distributional choices (e.g., Poisson, Negative Binomial) and more complex random effects structures (e.g., autoregressive). **Effect Size Estimation:** This pilot will provide critical data necessary to inform power analyses for a later efficacy trial. While effect sizes from pilot studies can have large standard errors and be unstable, we can use pilot data to estimate point estimates and confidence intervals for treatment effect sizes using the R package MBESS. The effect size of choice will be the standardized regression coefficient corresponding to the treatment group indicator in a model adjusted for the baseline measurement, which will have the same interpretation as the standardized mean difference (commonly referred to as Cohen's D). This analysis will provide a basis for calculating the minimal sample size required for a fully powered study while accounting for uncertainty in the effect size estimate.

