
Other exploratory analyses. ***Other Outcomes:*** We will use the framework described above for alcohol outcomes to analyze other behavioral outcomes (cannabis, NMPDU). ***Moderation:*** To assess potential moderators (e.g., sex, age) we will include interactions with treatment group in the GLMM models above. ***Mediation:*** To test if alcohol motives and other variables (e.g., mental health) mediate treatment effects, we will use Imai's causal mediation analysis framework, implemented in the R package *mediation*. Traditional mediation analysis is limited by the class of statistical models (e.g. the linear structural model of Baron and Kenny) that can be accommodated. Under technical assumptions of sequential ignorability, mediation effects are identifiable using Imai's framework when models for the mediator and outcome are non-linear, have discrete or continuous outcomes, include random effects, or are non-parametric. ***Engagement:*** Counts from Snapchat message logs (e.g., content viewed, replies), will be assessed descriptively to see types of content with high response and to measure dose. We will test for sex and age differences in engagement. ***Cost:*** We will calculate summary statistics for the total intervention-specific costs and mean costs per participant, with confidence intervals. Costs will be reported with/without start-up and development, for example, including costs for recruiting and training coaches and clinical supervision. As with [name] prior work, net costs (savings) will be calculated by subtracting mean costs per participant in the control group from costs per participant for the assigned condition, also calculating the incremental cost effectiveness ratio (difference in mean intervention cost vs. control divided by difference in mean effectiveness between intervention and control). Change in health benefits will be quantified as the difference in alcohol consequences per month for the

intervention vs. control, expressed in dollars per consequence averted. Sensitivity analyses to evaluate alternate assumptions for estimated costs will be conducted. Given likely skewness, we will identify appropriate ways to generate confidence intervals that do not rely on a normal distribution (e.g., non-parametric boot-strapping).

Power Analysis.

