For exploratory analyses regarding intervention efficacy, our inferential target (the regression coefficient corresponding to treatment group) is effectively equivalent to the comparison of two means, for which Cohen's D is the typical effect size (0.2: small; 0.5: medium; 0.8: large). Under the expected sample size ($n = 50-52$ per group), we will have sufficient power ($>80\%$) to detect effects on outcomes at a single time point if $D > 0.56$, a medium effect size. In analyses involving multiple follow-ups, the effective sample size cannot be smaller than the nominal sample size ($n = 50-52$ per group), and so the effect size of $D = 0.56$ is conservative in that case.

12. Provide the study stopping rules part of the study protocol. Generally, stopping rules reflect one of the following conditions: 1) there is clear evidence of harm; 2) there is no likelihood of demonstrating treatment benefit (futility); 3) there is overwhelming evidence of the benefit of treatment.

The PI will work directly with NIAAA, in the case that project discontinuation is necessary. Should there be clear evidence of harm to the participants due to this trial we will cease the trial. Given this is a no more than minimal risk study as deemed by our IRB, we do not anticipate evidence of harm. As this is a pilot/feasibility trial, we may not be able to detect a treatment effect and thus do not anticipate stopping the trial due to evidence of futility or benefit.

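### The mixed model adjusts for baseline at 2 months only, to cure an overestimation that does not arise, and leaves its 4-month effect unadjusted

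*Combined protocol and SAP*

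**What the plan says.** DSMP item 11, Testing for Intervention Effects, models the 2-month and 4-month outcomes jointly. The initial form is a Gaussian mixed model with a random intercept. The plan accepts baseline adjustment as protection against regression to the mean, but holds that "such adjustment at every time point may overestimate the treatment effect when there are multiple follow-ups". Its remedy is that "Baseline adjustment at only the first follow-up (2M in this case) corrects this overestimation", and it adopts this. It then says: "Overall, this approach is effectively the same as the ANCOVA method of RCT analysis", with an extension to several follow-ups. Time-by-group terms are to show whether the effect grows or fades.

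The Power Analysis paragraph names the group coefficient as the target: "our inferential target (the regression coefficient corresponding to treatment group". Other exploratory analyses applies the same framework to cannabis and NMPDU, and for moderators "we will include interactions with treatment group in the GLMM models above".

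Two analyses in the same section do use baseline: the initial t-test on pre-post differences, and the effect-size model. The point below concerns the mixed model only.

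**The concern.** The adjusting value is collected before randomisation. Conditioning on such a value at every follow-up does not bias a randomised comparison in the planned linear model, and the plan offers no derivation to the contrary. If the premise fails, the rule discards information at 4 months for no return.

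Four things are then at stake:

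- The 4-month effect from the mixed model carries the full chance imbalance in baseline.
- The pooled coefficient, which is the stated target, is only partly adjusted.
- The time-by-group contrast compares a partly adjusted effect with an unadjusted one.
- The description as ANCOVA is wrong for 4 months, where ANCOVA would include baseline.

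**Working it through.** **Inputs.** Sample size is from Aim 2 Methods: "intervention versus a control group (n=50-52 per group) among EAs with HID (balanced on sex and age group". I use 51 per arm, so k = 2/51 = 0.0392. The outcome SD is 1. The documents state neither alpha nor any correlation, so I assume two-sided 5%, complete Gaussian data and a range of correlations, written as baseline–2M / baseline–4M / 2M–4M.

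**1. The plan's own figure.** Power at D = 0.56 is Φ(0.56/√(2/n) − 1.96) = 80.0%, 80.7% and 81.5% for n = 50, 51 and 52 (noncentral t: 79.2%, 80.0%, 80.7%). The stated figure reproduces. It assumes no baseline adjustment, so the rule does not undermine it.

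**2. The premise.** I used 4,000 simulated trials in each of seven correlation settings, fitted by random-intercept REML with baseline at both visits. The mean pooled estimate was 0.498 to 0.506 for a true 0.5, and −0.003 to 0.005 for a true 0. The largest deviations also appear in the unadjusted analysis of the same data. No overestimation was found.

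**3. Time-specific 4-month effect.** With a baseline term in the 2-month rows only and time-by-group terms, the 4-month coefficient equalled the raw difference in 4-month means to rounding error. Hence:

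- SE under the rule: √0.0392 = 0.198, whatever the correlation.
- SE with baseline at both visits and a baseline–4M correlation of 0.5: √(0.75 × 0.0392) = 0.171.

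At 0.5/0.5/0.6 the simulated SDs were 0.202 and 0.177, and power at 0.5 SD was 73% and 81% (change-score t-test 70%).

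**4. Pooled effect at 0.5/0.5/0.6.** Let d0, d2 and d4 be the arm differences at baseline, 2M and 4M. The pooled estimate is (d2 − b·d0 + d4)/2. The fitted slope satisfies b = 0.5 − 0.5ρ, where ρ = (0.6 − 0.5b)/v and v is the mean of (1 − b + b²) and 1. The solution is b = 0.235, ρ = 0.530, v = 0.910.

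- Slope of the pooled effect on imbalance: (0.5 − 0.235 + 0.5)/2 = 0.3825.
- Variance of the two-visit mean: (1 + 0.6)/2 = 0.80; given baseline, 0.80 − 0.25 = 0.55.
- SE unadjusted: √(0.80k) = 0.177.
- SE with both visits: √(0.55k) = 0.147.
- SE with 2M only: √((0.55 + 0.3825²)k) = 0.165.
- Share of the variance gain lost: 0.3825²/0.25 = 59%.
- Model-based SE of the 4-month effect under the rule: √(0.910k) = 0.189, against a true 0.198.

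The three pooled SEs and the 0.189 match the simulation.

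**5. Other settings.** Simulated pooled power at a true 0.5 SD:

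| Correlations | Both visits | 2M only |
|---|---|---|
| 0.3/0.3/0.5 | 87% | 85% |
| 0.4/0.4/0.5 | 90% | 86% |
| 0.5/0.5/0.5 | 95% | 89% |
| 0.5/0.5/0.6 | 92% | 84% |
| 0.6/0.4/0.6 | 92% | 87% |
| 0.6/0.6/0.7 | 94% | 83% |
| 0.7/0.7/0.7 | 98% | 85% |

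The share of the pooled variance gain lost is 36% to 69%.

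**6. Error rates under no effect** (Monte Carlo SE 0.34 points). In the six settings with equal baseline correlations, the 4-month test rejects 5.2% to 7.1% under the rule and 4.1% to 5.2% with both visits. The pooled test (4.5% to 5.8%) and the time-by-group test (4.5% to 5.7%) stay near nominal under the rule.

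**7. Chance imbalance.** The SE of the baseline difference is 0.198 SD, so 0.2 SD is an ordinary imbalance. At 0.5/0.5/0.6 it moves the 4-month effect by 0.5 × 0.2 = 0.10 SD, the pooled effect by 0.3825 × 0.2 = 0.08, and the time-by-group term by 0.235 × 0.2 = 0.05. Under Specific Aim 2 the balance check acts only on significant differences: "If significant differences that could confound treatment effect estimates emerge, we will adjust for those variables or stratify analyses". At 51 per arm that needs about 1.98 × 0.198 = 0.39 SD.

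**The case against.** The strongest reply is that little hangs on this. The primary outcomes are feasibility and acceptability, analysed descriptively, and efficacy is exploratory. The planned estimator is unbiased, and pooled power under the rule is still 83% to 89% at 0.5 SD. The change-score test and the effect size meant for the later trial already use baseline. All of that stands and limits the severity. It does not supply a reason for the rule or repair the joint model.

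The correlations are assumed and may be generous for HID, whose pre-treatment value is also the eligibility item; selection on it could weaken the correlation. At 0.2/0.2/0.5 pooled power is 84% against 83%, which is negligible. HID frequency may also need a count model, which was not simulated. So the size is uncertain, but there is no offsetting benefit from the rule.

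Not all the excess 4-month rejection comes from the rule. At 0.6/0.4/0.6 it is 7.6% with 2M only and 6.8% with both visits, so much of it there reflects the equal-variance random-intercept form. The plan already intends to examine that form through diagnostics.

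The section also allows confounders to be added as covariates if a need is found. That clause is discretionary, and using it to put baseline in at 4 months would contradict the 2-month-only rule.

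Finally, the plan says only that overestimation may occur, and gives no equation. Adjusting the 4-month outcome for the 2-month value is conceivable, but the text does not describe it, and it would condition on a post-randomisation value.

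**Conclusion.** The concern holds for the mixed model and should be fixed. The overestimation rationale is wrong for a pre-randomisation covariate in the planned linear model. With complete data the rule makes the time-specific 4-month effect exactly unadjusted, and it forfeits roughly 36% to 69% of the precision gain in the pooled effect over the settings examined. At 0.5/0.5/0.6 this costs about 8 points of power for each effect. These sizes rest on assumed correlations, complete Gaussian data and 51 per arm; with missing visits the 4-month equality would be approximate.

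There is no bias on average, no damage to the stated power, and no effect on the primary outcomes. The loss is precision, protection against chance imbalance, and consistency with the plan's own account of the method as ANCOVA.

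**What to change.** Delete the two sentences on overestimation and its correction. In their place, state that:

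- the pre-randomisation value of the outcome enters as a covariate at both 2M and 4M, with a baseline-by-visit term, alongside visit and group;
- the group coefficient is the pooled effect;
- adding group-by-visit gives the 2M and 4M effects and the time-by-group test;
- the same form applies to the other behavioural outcomes and the moderator models.

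Name the value used as baseline. Table 1 (Measures) lists "Past-Month HID (eligibility criteria) based on MTF" at screening, post-test and follow-up, not in the baseline survey. The screening value is therefore the one available for HID and for other outcomes collected at screening; the baseline-survey value serves for the rest.

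The cost is a few sentences of analysis-plan text and one extra model term. No new data are needed, and the model would then fit the plan's ANCOVA description.

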Intervention period. The Study Coordinator will review Snapchat message logs for accuracy and consistency after close of each intervention wave; note weekly supervision with [name]/[name] will also include review of message logs.

Follow-up Assessments. Monthly, the Data Manager and Study Coordinator will review follow-up data for accuracy and out of range values; ensure that all follow-up data are backed-up; insure that all follow-up interviews are accounted for in the tracking database; update flow chart to ensure accurate numbers of follow-up assessments recorded as completed, missed, refused, or withdrawn.

Protecting Confidentiality

To minimize the risk of violating confidentiality, RAs will make every effort to ensure that study data are always kept confidential. Research staff will sign a pledge of confidentiality and will understand that violation of confidentiality is reason for dismissal. Staff training procedures will include information about the importance of confidentiality and techniques to maintain confidentiality of all information reported by research participants. Staff will maintain human subjects and confidentiality certifications through the U-M Program for Education and Evaluation in Responsible Research and Scholarship system and will complete CITI Good Clinical Practice Training. Consent documents will fully explain the study procedures, potential risks, and potential benefits.

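### The power statement treats all 102 enrolled participants as analysed, leaving no room for missed follow-up, and its claim about effective sample size omits a condition.

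*Combined protocol and SAP*

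**What the plan says.** The Enrollment paragraph under Aim 2 Methods states: "Target enrollment is 102 EAs (approximately 50% males and 50% females) between the ages of 18-25". It gives 50-52 per group for the two arms. Participants are randomised after completing baseline, so any loss at 2 or 4 months comes out of that number.

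The Power Analysis in item 11 of the Data Safety Monitoring Plan uses the same figure: "Under the expected sample size ($n = 50-52$ per group), we will have sufficient power", given as above 80% for D above 0.56 at a single time point. For analyses with both follow-ups it adds that "the effective sample size cannot be smaller than the nominal sample size", again 50-52 per group, and on that ground calls 0.56 conservative.

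Three other places bear on the number analysed:

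- Item 9, Follow-up Assessments, plans a flow chart with "accurate numbers of follow-up assessments recorded as completed, missed, refused, or withdrawn".
- Item 11, Specific Aim 2, says "randomized participants will be included in intent-to-treat analyses, regardless of engagement".
- Item 11, Testing for Intervention Effects, starts with "basic two-sample comparisons, operating on the pre-post differences (e.g., 4M-Baseline) to test for treatment effects", with a two-sample t-test as first choice, and then describes mixed models for the 2-month and 4-month outcomes together.

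No retention rate, inflation of the sample size or imputation method is stated. Alpha is not stated either.

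**The concern.** A power figure for a single follow-up should rest on the number expected to have an outcome at that follow-up. Here it rests on the number enrolled, although the plan itself provides for missed, refused and withdrawn assessments.

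The intent-to-treat sentence does not close the gap. It concerns engagement with the intervention. A 4-month minus baseline difference cannot be formed for someone with no 4-month survey. A mixed model can use a participant with one follow-up, but has no outcome for one with none.

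The effective-sample-size sentence has a related gap. A second correlated measurement adds information for people who are measured, but it cannot make up without limit for people who are never measured. At stake is whether the reader is told the effect that the trial can detect with the data it is likely to have.

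**Working it through.** **Inputs.** From the documents: 102 enrolled, 50-52 per group, D = 0.56, power above 80%, two follow-ups. Assumed, because the documents do not give them: two-sided 5% level, retention of 70% to 95%, the baseline to follow-up correlation r, and the 2-month to 4-month correlation ρ.

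**Step 1: reproduce the stated figure.** For a two-sample t-test with SD 1, power comes from a noncentral t with n1 + n2 − 2 degrees of freedom and noncentrality D / √(1/n1 + 1/n2). For 51 per arm this is 0.56 × √(51/2) = 2.83 on 100 degrees of freedom.

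| Analysed per arm | Power at D = 0.56 | D detectable at 80% |
|---|---|---|
| 50/50 | 79.2% | 0.566 |
| 50/52 | 80.0% | 0.560 |
| 51/51 | 80.0% | 0.560 |
| 52/52 | 80.7% | 0.555 |

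The stated 0.56 is the value for 102 participants with complete data. A one-sided 5% test would give 87-88% power and a detectable D of 0.49-0.50, so two-sided 5% is the reading that matches the plan.

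**Step 2: allow for missed follow-up at one time point.** Analysed number per arm = 51 × retention.

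| Retention (assumed) | Analysed per arm | Power at D = 0.56 | D detectable at 80% |
|---|---|---|---|
| 95% | 48.45 | 77.9% | 0.575 |
| 90% | 45.9 | 75.6% | 0.591 |
| 85% | 43.35 | 73.2% | 0.609 |
| 80% | 40.8 | 70.5% | 0.628 |
| 70% | 35.7 | 64.5% | 0.672 |

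**Step 3: see what the baseline measurement does.** In units of the outcome SD, the detectable difference is multiplied by √(1 − r²) with baseline as a covariate. For the t-test on pre-post differences, with equal SDs over time, the factor is √(2(1 − r)).

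| r (assumed) | Covariate, 100% | Covariate, 80% | Pre-post difference, 100% | Pre-post difference, 80% |
|---|---|---|---|---|
| 0.3 | 0.53 | 0.60 | 0.66 | 0.74 |
| 0.5 | 0.49 | 0.54 | 0.56 | 0.63 |
| 0.7 | 0.40 | 0.45 | 0.43 | 0.49 |

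With baseline as covariate, the r that brings the detectable difference back to 0.56 is about 0.32 at 90% retention and 0.45 at 80%. The pre-post t-test needs r above 0.5 before it does better than an unadjusted comparison.

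**Step 4: test the effective-sample-size sentence.** Let p0, p1 and p2 be the shares giving no, one and two follow-ups. With equal SDs and a random intercept, a participant with two visits counts as 2/(1 + ρ) single measurements, so

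effective n = n × [p1 + 2 × p2 / (1 + ρ)].

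If p0 = 0, the bracket is at least p1 + p2 = 1 for any ρ up to 1, and the plan's sentence is true. Since p0 + p1 + p2 = 1, effective n falls below n exactly when p0 > p2 × (1 − ρ)/(1 + ρ). With n = 51 and ρ = 0.7:

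| Miss both | Miss one | Calculation | Effective n |
|---|---|---|---|
| 0% | 40% | 51 × (0.40 + 1.20/1.7) | 56.4 |
| 10% | 0% | 51 × 1.80/1.7 | 54.0 |
| 10% | 10% | 51 × (0.10 + 1.60/1.7) | 53.1 |
| 15% | 0% | 51 × 1.70/1.7 | 51.0 |
| 20% | 0% | 51 × 1.60/1.7 | 48.0 |

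If 20% miss both visits and the rest attend both, the crossing point is ρ = 0.60: effective n is 54.4 at ρ = 0.5 and 42.9 at ρ = 0.9. If 10% miss both, the crossing point is ρ = 0.80.

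**The case against.** The plan's figure is correct on its own condition: with 102 participants analysed, 0.56 is right. The power paragraph names the treatment coefficient as its target, and the effect-size paragraph takes that coefficient from a baseline-adjusted model. On that reading a moderate baseline correlation can absorb moderate loss; at 80% retention and r = 0.5 the detectable difference is 0.54. The effective-sample-size sentence can be read as the usual remark that a second outcome per person does not reduce information, and four of the five cases tabulated for ρ = 0.7 are at or above 51. The item 9 wording is routine tracking language, and the plan pays for follow-up surveys and sends reminders through several channels. The trial is a pilot with descriptive primary outcomes, and item 12 concedes that an effect may not be detected.

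Much of this stands, and it limits the point to a minor one. The arithmetic for complete data is not in dispute. Part of the larger figures for the pre-post t-test comes from change scoring rather than loss: at r = 0.3, 0.56 becomes 0.66 with complete data, and loss of 20% then takes it to 0.74.

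The core is not answered. The power paragraph does not invoke baseline adjustment or give a correlation, and reminders and payments are not a retention rate. The sentence on effective sample size is unconditional and is tied to 50-52 per group, which is the enrolled number.

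**Conclusion.** The concern holds, as a minor one. The stated power requires essentially all 102 participants to be analysed; even 5% loss takes unadjusted power at D = 0.56 to 77.9%. At 90% to 80% retention the detectable D is 0.59 to 0.63 rather than 0.56, before any gain from baseline adjustment. The statement that effective sample size cannot fall below nominal is not always false, but it is guaranteed only when every randomised participant gives at least one follow-up. It fails when enough participants miss both visits and the two follow-ups are highly correlated.

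These results rest on an assumed two-sided 5% level, assumed retention and correlations, and equal SDs over time for the pre-post and effective-n calculations. Neither the primary outcomes nor any stopping decision depends on them.

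**What to change.** Restate the power sentence by the number expected to be analysed, and state alpha. For example: at 80% power and two-sided 5%, the detectable D at a single time point is 0.56 if all 102 are analysed, 0.59 at 90% follow-up and 0.63 at 80%, before baseline adjustment. The team should say which follow-up rate it expects. If it wants to rely on baseline adjustment, it should give the assumed correlation.

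Limit the next sentence with the words: provided every randomised participant gives at least one follow-up. Alternatively, delete it together with the description of 0.56 as conservative.

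The cost is wording only. The stated detectable effect becomes slightly less favourable, and enrolment and analyses do not change.
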